10.3.6 Adverse Events of Special Interest

Adverse events of special interest are those that have been identified in preclinical studies, as well as known AEs from oligonucleotides as a drug class and those from the cobomarsen emerging AE profile from the Phase 1 study. These AEs of interest will be closely monitored, and specific dose interruption rules have been established. These include:

- Hematological: neutropenia, lymphopenia;
- Hepatic: increase transaminases, gamma-glutamyl transferase (GGT), bilirubin consistent with hepatic involvement;

- Renal: increase serum creatinine, blood urea nitrogen (BUN) and hematuria, proteinuria, consistent with kidney involvement;
- Increased TSH;
- Constitutional symptoms: acute fever, chills, myalgias, fatigue.

10.4 Adverse Event Classification

10.4.1 Relationship to Study Treatments

The Investigator's assessment of causality must be provided for all AEs (serious and non-serious). An Investigator's causality assessment is the determination of whether there exists a reasonable possibility that the investigational product caused or contributed to an AE.

- Not related: The AE is clearly not related or is unlikely to be related to the study treatment. The temporal relationship of the onset of the AE relative to administration of the product is not reasonable, or the AE can be explained by another cause such as an underlying medical condition or other concomitant therapy, or the AE has no plausible relationship to study therapy.
- Related: The AE is related to the study treatment. The temporal relationship of the AE to administration of the product is reasonable and there is no other cause to explain the event. AEs should be classified as related if the Investigator feels the event may reasonably be regarded as caused by, or probably caused by, the study treatment.

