2.1.3.2 Clinical Background

Cobomarsen is being evaluated in a Phase 1 clinical trial to investigate its safety, tolerability and PK, as well as exploratory measures of pharmacodynamics (PD) and efficacy in subjects with CTCL, mycosis fungoides subtype. The study has also enrolled a limited number of subjects with chronic lymphocytic leukemia (CLL), diffuse large B-cell lymphoma (DLBCL) and adult T-cell leukemia/lymphoma (ATLL). Details of the Phase 1 clinical trial results are provided in the cobomarsen (MRG-106) Investigator's Brochure.

Study MRG106-11-101 has completed enrollment of subjects who had prior treatment for CTCL, mycosis fungoides subtype, stages I, II or III. As of 23 July 2019, 6 subjects with CTCL have been treated in Part A with 75 mg cobomarsen by intratumoral injection, and 37 subjects with CTCL have been treated in Part B with 300, 600 or 900 mg cobomarsen by subcutaneous injection, or intravenous infusion or injection. Of note, 2 subjects that had completed Part A were re-enrolled in Part B (with new unique identification numbers) following an 8-week washout period, as permitted in the protocol. In addition, cobomarsen has been explored in other indications and at additional dose levels, as detailed in the Investigator's Brochure.

Overall, the study treatment has been well tolerated. The majority of AEs have been mild or moderate in severity (grade 1 or 2) and there have been no safety signals indicative of clinically significant adverse effects on renal, liver, coagulation, platelets or thyroid function at the dosing regimens evaluated to date. Two subjects experienced dose-limiting toxicities (pruritus and disease flare) resulting in study discontinuation, per protocol. Ninety-two percent (92%) of subjects treated with systemic administration showed improvement in skin disease as measured by the mSWAT score. Sixty-three percent (63%) of subjects treated with 300 mg IV infusion (5 of 8 subjects) achieved a partial response. Being well tolerated, this dose and mode of administration has been selected for the SOLAR trial. Full details on safety and efficacy of cobomarsen in CTCL are found in the Investigator's Brochure.

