10.3.2 Suspected Adverse Reaction

A suspected adverse reaction is any AE for which there is a reasonable possibility that the drug caused the AE. For the purposes of Investigational New Drug (IND) safety reporting, “reasonable possibility” means there is evidence to suggest a causal relationship between the drug and the AE. Suspected adverse reaction implies a lesser degree of certainty about causality than adverse reaction, which means any AE caused by a drug.

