10.5.2 Follow-up of Adverse Events

All AEs considered to be related to study treatment will be followed until resolution or stabilization.

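### Section 10.4.1 contains conflicting causality tests with no rule on which governs, so adverse events with a competing explanation may be under-called as related or coded differently across sites

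*Combined protocol and SAP*

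**What the plan says.** Section 10.4.1 asks the investigator to determine "whether there exists a reasonable possibility that the investigational product caused or contributed to an AE". It then offers two categories and no middle tier.

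- 'Not related' is headed by events that are clearly not, or are unlikely to be, due to treatment. Three alternatives joined by 'or' follow: unreasonable timing, no plausible relationship, or that "the AE can be explained by another cause such as an underlying medical condition or other concomitant therapy".
- 'Related' asks that the timing "is reasonable and there is no other cause to explain the event". Its last sentence adds that an AE should be so classified "if the Investigator feels the event may reasonably be regarded as caused by, or probably caused by, the study treatment".

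Section 10.3.2 has its own threshold: "A suspected adverse reaction is any AE for which there is a reasonable possibility that the drug caused the AE".

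On follow-up, Section 10.5.2 states: "All AEs considered to be related to study treatment will be followed until resolution or stabilization". Sections 7.2.1 and 10.5.1 require every AE to be reported up to 60 days after the last dose whatever its cause. Beyond that point, their explicit duty covers only treatment-related AEs. Section 12.4.5 tabulates treatment-related AEs using the investigator's attribution.

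**The concern.** A causality variable needs one test. Here the opening standard admits a drug contribution alongside other causes, the 'Related' criterion excludes any event that has another cause, and the 'Not related' criterion captures any event that another cause can explain. The events that need the most careful judgment, those with plausible timing and a rival explanation, are the ones on which the tests disagree. Several AEs of special interest in Section 10.3.6, such as fever, fatigue, lymphopenia and raised transaminases, could arise from intercurrent illness or co-medication as well as from treatment.

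With two categories only, a doubtful event has to go to one side or the other. Different sites may resolve the conflict differently. The trial is open-label, so investigators make this judgment knowing the treatment. If events are under-called, some non-serious AEs lose required follow-up, some late AEs lose an explicit reporting duty, and the treatment-related AE summary is too low.

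**Working it through.** The plan states no figure on this point, so the check is of wording and consequences.

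**Step 1: apply each test to one event.** Take an AE with plausible timing, a reasonable possibility that the drug contributed, and a competing explanation from disease or co-medication.

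| Test | Excludes other causes? | Counts contribution? | Result |
|---|---|---|---|
| 10.4.1, opening standard | No | Yes | Causal relationship |
| 10.3.2, suspected adverse reaction | No | Not stated | Suspected reaction, if there is a reasonable possibility that the drug caused it |
| 10.4.1, 'Related', timing and other-cause sentence | Yes | No | Not met |
| 10.4.1, 'Not related', other-explanation limb | Another explanation suffices | No | Not related |
| 10.4.1, 'Related', closing sentence | No | No | May be related, by judgment |

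One event thus receives opposite labels within one section. No sentence ranks the tests.

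**Step 2: trace what the label decides.**

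| Depends on the label | Does not depend on it |
|---|---|
| Follow-up of non-serious AEs to resolution or stabilization (10.5.2; Appendix B footnote j; Appendices C and E footnote m) | Follow-up of serious AEs (10.6.2) |
| Explicit duty to report AEs beyond 60 days (7.2.1, 10.5.1) | Reporting of all AEs and serious AEs up to 60 days (7.2.1, 10.5.1, 10.6.1) |
| Arguably post-trial reports, which use a 'caused by' phrase without citing 10.4.1 (10.7) | AE recording at long-term follow-up visits, which are for subjects who have not progressed (8.5.1, 9.3.1) |
| Treatment-related AE element of the secondary safety endpoint (3.2.2) and its table (12.4.5) | Tables of all AEs, serious AEs, grade 3 or 4 AEs and AEs leading to discontinuation (12.4.5) |

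**Step 3: does the period beyond 60 days matter?** Section 2.1.3.2 suggests a terminal half-life for cobomarsen of about 2.5 to 3 weeks, that is 2.5 × 7 = 17.5 to 3 × 7 = 21 days. Assuming simple first-order decline at that rate from the last dose:

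- at 17.5 days: 60 / 17.5 = 3.43 half-lives, and 0.5^3.43 = 0.09;
- at 21 days: 60 / 21 = 2.86 half-lives, and 0.5^2.86 = 0.14.

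About 9% to 14% would remain when the all-cause reporting window closes. This shows only that late drug-related events are conceivable. It does not estimate how many there would be.

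**The case against.** The best defence is that the closing sentence under 'Related' is the operative instruction. It is the only one that tells the investigator when to classify an AE as related, it carries no exclusion of other causes, and it agrees broadly with the opening standard and with Section 10.3.2. The heading of 'Not related' helps too: an event to which the drug may reasonably have contributed is not naturally described as clearly unrelated or unlikely to be related. Most safety reporting does not turn on the label, the endpoint affected is descriptive, and one definition serves both arms.

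Much of this stands, and it limits the point. It does not remove it: the closing sentence omits contribution, leaves the other-cause condition and the other-explanation limb in place, and is not said to override them.

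Four stronger readings are tempting but unsupported.

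- *Such events must be coded 'Not related'.* The closing sentence allows the opposite.
- *The rule would have missed both Phase 1 dose-limiting toxicities.* Section 2.1.3.2 says only: "Two subjects experienced dose-limiting toxicities (pruritus and disease flare) resulting in study discontinuation, per protocol". It gives neither the causality criteria used nor any alternative cause. In this trial, moreover, such events would be recorded up to 60 days whatever the label, and AEs leading to discontinuation are tabulated without regard to cause.
- *Follow-up and late capture stop once an event is called unrelated.* The right-hand column of the second table contradicts this.
- *The wording biases the comparison between arms.* The open-label design makes differential coding possible, but nothing in the documents shows it.

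**Conclusion.** The inconsistency is real and visible within Section 10.4.1. Its effect is a risk of under-called relatedness and of inconsistent coding, confined to the left-hand column of the second table. The number of events affected cannot be estimated: the documents give no AE counts by attribution. Neither the primary endpoint nor progression-free survival, the key secondary endpoint, is touched. This is a wording conflict worth correcting, not a defect that threatens the trial's main conclusions.

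The conclusion assumes that sites apply Section 10.4.1 as printed. The eCRF completion guidelines and the SAE form are not among the documents, and clear instructions there could reduce the risk. It also matters that a contribution judgment that was never recorded cannot be reliably reconstructed at analysis.

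**What to change.** Bring Section 10.4.1 into line with its own opening standard:

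- Remove the other-cause condition from 'Related'.
- Define 'Related' as a reasonable possibility that study treatment caused or contributed to the event, even if another cause may also have contributed.
- Limit 'Not related' to events with no reasonable possibility of a causal contribution from study treatment.
- Put the same wording in the eCRF guidance.

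The cost is an amendment that rewrites both category definitions, the guidance update, and a short notice to sites. If events have already been coded under the present wording, sites should be asked to review those with a recorded alternative cause, so that the treatment-related table does not mix two definitions. The downside is a somewhat higher count of treatment-related AEs. No sample size or efficacy analysis changes.

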10.4.2 Severity

All AEs entered into the eCRF will be graded for severity using the NCI CTCAE, version 5.0. If an AE is not listed in the CTCAE version 5.0, then the Investigator will use the terms: Mild, Moderate, Severe, or Life-threatening to describe the maximum intensity of the AE. For purposes of consistency, these intensity grades are defined as follows:

Severity	Definition
Grade 0	No change from Normal or Reference Range
Grade 1 (Mild)	No limitation of usual activities.
Grade 2 (Moderate)	Some limitation of usual activities.
Grade 3 (Severe)	Inability to carry out usual activities.
Grade 4 (Life-threatening)	Immediate risk of death.
Grade 5 (Death)	Resulting in death

10.5 Collection and Reporting of Adverse Events

10.5.1 Reporting of Adverse Events

Subjects will be evaluated and questioned generally to identify AEs during the course of the study. Any AEs occurring prior informed consent will be recorded on the Medical History eCRF. All AEs from the time of informed consent, including those deemed to be related to a study procedure, should be reported on the Adverse Event eCRF. All AEs, including SAEs, will be reported from the time of informed consent. All events occurring after administration of the first dose of study treatment or those that increase in severity or frequency will be considered treatment-emergent adverse events (TEAEs). Adverse events that occur from the time of informed consent up to and including 60 days after the last dose of study treatment, regardless of causality to study treatment, must be reported. Any treatment related AE reported by a subject during the clinical study, even if it occurs later than 60 days after the last dose of study treatment, should be reported in the eCRF.

All AEs spontaneously reported by the subject and/or in response to an open question from study personnel or revealed by observation, physical examination, or other diagnostic procedures will be recorded on the Adverse Event eCRF. Clinically significant changes in vital signs and clinically significant findings on physical examination will be recorded as AEs.

Any clinically significant change in laboratory assessments or other clinical findings, as assessed by the Investigator, is considered an AE and must be recorded on the Adverse Event eCRF. In addition, an abnormal test finding will be classified as an AE if one or more of the following criteria are met:

- The test finding is accompanied by clinically significant symptoms;
- The test finding necessitates additional diagnostic evaluation(s) or medical/surgical intervention; including additional concomitant drug treatment or other therapy. Note: simply repeating a test finding, in the absence of any of the other listed criteria, does not constitute an AE;
- The test finding leads to a change in study treatment dosing or discontinuation of subject participation in the clinical research study;
- The test finding is considered an AE by the Investigator.

Wherever possible, a specific disease, diagnosis or syndrome rather than individual associated signs and symptoms should be identified. However, if an observed or reported sign or symptom

is not associated with a documented disease or syndrome, the sign or symptom should be recorded as a separate AE. Laboratory data are to be collected as stipulated in this protocol. Clinical syndromes associated with laboratory abnormalities are to be recorded as appropriate (e.g., diabetes mellitus rather than hyperglycemia).

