Analysis of cobomarsen clinical PK data reveal biphasic plasma concentration time curves, indicative of multi-compartmental pharmacokinetics. Apparent half-lives ($t_{1/2}$) measured over the first 24-hours were similar for all routes of administration (ROA), ranging from 5.0 to 8.2 hours. Trough plasma samples collected once a month during prolonged administration of cobomarsen generally increased from the first extension cycle sample collection over the next one to two cycles, where they achieved maximum concentrations and then plateaued or declined over subsequent cycles. This may indicate steady state concentrations being achieved after 3 or 4 cycles of dosing, or after approximately 12-16 weeks of regular cobomarsen administration, suggesting a terminal elimination half-life of approximately 2.5 to 3 weeks. Despite the observed differences in C_{max} and T_{max} , dose normalized systemic exposure ($AUC_{0-24}/Dose$) for all dose levels in the intratumoral, subcutaneous, and intravenous 2-hour infusion cohorts were similar, demonstrating good dose proportionality across those ROAs and dose concentrations. Accumulation ratios (multiple dose $C_{max}/$ first dose C_{max} or multiple dose $AUC_{0-24}/$ first dose AUC_{0-24}) indicated no significant accumulation at the 900 mg dose level for any route of administration. For full details on PK profile of cobomarsen in CTCL, please refer to the Investigator's Brochure.

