5.3 Lifestyle Guidelines

5.3.1 Contraception Guidelines

Female subjects must be either postmenopausal (absence of menses) for at least 1 year and have menopause confirmed by follicle-stimulating hormone (FSH) levels, or must be postmenopausal for at least 2 years (over 50 years old and absence of menses for 2 years, no confirmation by FSH required), or must be surgically sterile for at least 6 weeks, or must agree to take appropriate precautions to avoid pregnancy from Screening up to and including 105 days after the last dose of cobomarsen or 180 days after the last dose of vorinostat, if of childbearing potential.

Males must agree to take appropriate precautions to avoid fathering a child from Screening up to and including 105 days after the last dose of study treatment and must consent to using an acceptable method of contraception such as a condom and a highly effective second method

(examples provided below), surgical sterilization (by one of the partners), postmenopausal partner (meeting the definition above), or abstinence.

The following methods have been determined to be highly effective (< 1% failure rate per year when used consistently and correctly) ([Trussell 2004](#); [Clinical Trial Facilitation Group 2014](#)) and are permitted under this protocol for use by the subject and his/her partner:

- Complete abstinence from heterosexual intercourse during the entire period of risk associated with the study treatments, when this is in line with the preferred and usual lifestyle of the subject;
- Oral, intravaginal, or transdermal combined (containing estrogen and progestogen) hormonal contraception associated with inhibition of ovulation;
- Oral, injectable, or implanted progestogen-only hormonal contraception associated with inhibition of ovulation;
 - Note: Progestogen-only “mini-pills” are not considered highly effective methods of contraception for this protocol because inhibition of ovulation is not their primary mechanism of action.
- Intrauterine device (IUD);
- Intrauterine hormone-releasing system (IUS)
- Vasectomy or vasectomized partner, provided that the partner is the sole sexual partner of the female trial participant and that the vasectomized partner has received medical assessment of the surgical success;

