7.2 Safety Assessments

7.2.1 Adverse Events

AEs will be assessed at each study visit (in person or by telephone for telephone visits) by direct observation and subject interviews. The severity of AEs will be evaluated using the NCI CTCAE version 5.0. All AEs that occur from the time of informed consent up to and including 60 days after the last dose of study treatment, regardless of causality to study treatment, must be reported. Any treatment related AE reported by a subject during the clinical study, even if it occurs later than 60 days after the last dose of study treatment, should be reported in the eCRF.

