8.3 Post-treatment

The following are the definitions for post-treatment visits in this study:

- **End of Treatment:** Time at which the subject is permanently discontinued from study treatment for any reason.
 - The End of Treatment Visit should be performed as soon as possible but ≤ 14 days after the last dose of study treatment. See [Section 8.4](#) for End of Treatment visit requirements.
- **Follow-up:** The subject has completed study treatment but remains on study and is being followed for response and/or progression.
 - Subjects who had an ongoing response or stable disease at the time that they discontinued study treatment must continue to be followed for response and/or disease progression in the Follow-up Period. See [Section 8.5](#) and [8.6](#) for the follow-up visit frequency and requirements.
- **End of the Study:** The subject has completed all required follow-up on study and is no longer being followed for response or disease progression, in the study period.
 - If a subject withdraws consent for further follow-up at any time on study, the End of Study date is the date that consent is withdrawn.

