8.4 End of Treatment Visit

At the time of study treatment discontinuation, the End of Treatment Visit should be completed for all subjects after the last dose of study treatment, and every effort should be made to perform the procedures listed below. This visit should take place as soon as possible and ≤ 14 days after the last dose of study treatment. The date and reason for stopping the study treatment will be reported. The End of Treatment visit is not considered as the end of the study. All subjects will enter the Follow-up unless they have withdrawn their consent to do so.

- Perform CTCL disease evaluation using the mSWAT (see [Appendix F](#)).
- Obtain vital signs (blood pressure, heart rate, respiratory rate, and body temperature).
- Perform a brief, symptom-directed physical examination (including documentation of weight).
- Collect blood for the following:
 - Hematology;
 - Clinical chemistry;
 - TSH;
 - Cobomarsen group only: PD and ADA
 - Cobomarsen group only: PK.
- Collect urine for the following:
 - Urinalysis;
 - Pregnancy test (for females of childbearing potential).
- Perform a single 12-lead ECG.
- IWRS Transaction (Discontinue the Subject in the System).
- Review and record AEs and concomitant medications.

8.5 Long-term Follow-up for Subjects Who Have Not Progressed at the Time of End of Treatment Visit

After the End of Treatment Visit, subjects who did not progress on study will be followed until progression (confirmed progression in skin, confirmed loss of response in skin or clinical progression in lymph nodes, blood or viscera assessed per investigator discretion), withdrawal of

consent, initiation of subsequent MF treatment, loss to follow-up, or death, and the subject's final disposition is documented and reviewed by the Sponsor study team.

8.5.1 Every-4-Week Assessment through Week 81, then Every-8-Week Assessments Thereafter (± 3 Days)

- Perform CTCL disease evaluation using the mSWAT (see [Appendix F](#)).
- Review and record AEs and concomitant medications.

8.6 Follow-up Visit 28 ± 5 days after the End of Treatment or Early Termination

For subjects who choose not to participate in the crossover period of the study (or delay the start of the crossover period by > 28 days) or who discontinue cobomarsen treatment, the following assessments will be performed 28 ± 5 days after the End of Treatment Visit (assuming the subject has not withdrawn consent).

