10.6 Collection and Reporting of Serious Adverse Events

10.6.1 Initial Serious Adverse Event Reports

All SAEs that occur from the time of informed consent up to and including 60 days after the last dose of study treatment must be reported by the Investigator to the Sponsor or Sponsor's designated representative immediately, and in no circumstances later than 24 hours after gaining awareness of the event by submission of a SAE Notification Form. Investigators must report to the Sponsor or the Sponsor's designated representative any SAE, whether or not considered drug related, including those listed in the protocol or Investigator's Brochure. The initial report must contain at a minimum a subject identifier code, an event term, and an assessment of causality. The SAE Notification Form should be faxed or e-mailed to:

[REDACTED]
[REDACTED]
[REDACTED]
[REDACTED]

If the Investigator is unable to complete and send the SAE Notification Form within the timeframe required, the SAE must be reported via phone call to the Medical Monitor (see contact sheet in the study reference binder) and [REDACTED].

An Investigator may be requested by the Sponsor or the Sponsor's designated representative to obtain specific follow-up information in an expedited fashion. This information may be more detailed than that captured on the Adverse Event eCRF. In general, this will include a description of the SAE in sufficient detail to allow for a complete medical assessment of the case and independent determination of possible causality. Information on other possible causes of the event, such as concomitant medications and illnesses must be provided. In the case of a subject

death, a summary of available autopsy findings must be submitted as soon as possible to the Sponsor or the Sponsor's designated representative.

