- a) Follow-up visit assessments to be performed 28 days after the last dose of study treatment and for subjects who discontinue treatment early (if the subject has not withdrawn consent).
- b) Subjects who did not progress on study will continue to be followed for response and progression every 4 weeks through Week 81, then every 8 weeks.
- c) Day 1 refers to the first dosing day.
- d) mSWAT assessment will be completed prior to dosing when applicable, at the indicated visits. The Day 1 evaluator should conduct all subsequent mSWAT evaluations.
- e) Complete physical examination on Day 1 or within 2 days prior to the Day 1 visit; brief physical examination at all subsequent time points.
- f) To be collected on Day 1 (predose and within the 10 minutes before the end of the infusion) and on Day 2 (24 ± 4 hours after Day 1 dosing).
- g) To be performed predose and as soon as possible postdose (ideally within 30 minutes of the end of the infusion) on Days 1 and 29, and predose on indicated study days, and at the follow-up visit. If the subject has an elevated QTcF during study treatment defined as (QTcF > 450 msec for males or > 470 msec for females or > 480 msec for subjects with bundle branch block, please see [section 7.2.3](#) for additional guidance.
- h) Hematology, clinical chemistry, TSH and urinalysis (including microscopy) as indicated in the protocol will be collected predose on each of the indicated study days. Laboratory assessments do not need to be performed on Day 1 if Screening laboratory measurements were performed within 3 days prior to Day 1.
- i) Coagulation assessments (PT, aPTT, and INR) are to be performed on Day 1 predose and at 3 hours (± 10 minutes) postdose; on Day 2; on Day 8 predose; on Day 29 predose; and at the follow-up visit.
- j) All AEs, including SAEs, will be reported from the time of informed consent up to and including 60 days after the last dose of study treatment. Treatment-related AEs ongoing at the end of treatment or follow-up visits should be followed to resolution or until the investigator considers them “chronic” or “stable.”
- k) All medications (including over-the-counter medicines, herbal treatments, supplements, and vitamins) administered 30 days before the first administration of study treatment (Day 1) until the end of the study should be recorded on the eCRF.

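### Adverse events are due to 60 days after the last dose, but progressors not on crossover dosing have no planned contact for the last 13 to 37 of those days

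*Combined protocol and SAP*

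**What the plan says.** Sections 7.2.1 and 10.5.1 set the collection window for adverse events of any cause: "Adverse events that occur from the time of informed consent up to and including 60 days after the last dose of study treatment" have to be reported. Section 10.6.1 applies the same limit to serious events: "All SAEs that occur from the time of informed consent up to and including 60 days after the last dose of study treatment" go to the sponsor within 24 hours of awareness. Section 7.2.1 has adverse events assessed at study visits, in person or by telephone.

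Three kinds of contact are planned once dosing ends:

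- **End of Treatment Visit.** Section 8.3: "The End of Treatment Visit should be performed as soon as possible but ≤ 14 days after the last dose of study treatment".
- **Follow-up Visit.** Section 8.6: "the following assessments will be performed 28 ± 5 days after the End of Treatment Visit". Section 9.3.2 and the column headers of Appendices B, C and E use the same starting point. Footnote a of Appendix B uses another: "Follow-up visit assessments to be performed 28 days after the last dose of study treatment". Footnote b of Appendix C and footnote a of Appendix E also count from the last dose.
- **Long-term follow-up.** Sections 8.5 and 9.3 provide 4-weekly contacts through Week 81, then 8-weekly, each with adverse-event review, but only for subjects who have not progressed.

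Section 8.6 exempts vorinostat subjects who start crossover without a delay of more than 28 days. They move to the visit schedule of Section 9.2.2.

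**The concern.** The reporting window is mandatory, yet no visit or call at or after Day 60 appears in Sections 8 to 10 or in Appendices B, C or E for a subject who has progressed and is not on crossover dosing. Three groups are affected: cobomarsen subjects who progress in the randomized period, subjects who progress in the crossover period, and vorinostat subjects who progress and do not cross over.

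Safety and tolerability of cobomarsen is the first secondary objective listed in Section 3.1.2. Section 10.5.1 defines treatment-emergent events with no upper time limit, and Section 12.4.5 tabulates them, so late events belong in the main safety tables. Section 2.1.3.2 describes slow terminal elimination, "suggesting a terminal elimination half-life of approximately 2.5 to 3 weeks", which makes events after the Follow-up Visit plausible.

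The gap is also uneven. A subject who stops for toxicity without progression keeps scheduled review (Sections 8.5 and 10.2.2), while a progressor does not. Only vorinostat progressors can cross over, and Section 12.5.2 assumes median progression-free survival of 4 months on vorinostat against 8 on cobomarsen. The mix of observed and unobserved follow-up may therefore differ between arms.

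**Working it through.** The plan states no figure for this gap, so the check is calendar arithmetic on its own visit windows.

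**Inputs.** Window: 60 days after the last dose (10.5.1, 10.6.1). End of Treatment Visit: Day 0 to 14 (8.3). Follow-up Visit: 28 ± 5 days, that is 23 to 33 days, after the starting point (8.6, 9.3.2, appendix headers and footnotes).

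**Formulas.** Last planned contact = starting day + 23 to 33. Gap = 60 − last planned contact.

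1. *Counted from the End of Treatment Visit (8.6, 9.3.2).* Earliest 0 + 23 = Day 23; latest 14 + 33 = Day 47. Gap: 60 − 47 = 13 days to 60 − 23 = 37 days. Shares: 13/60 = 22% and 37/60 = 62%.
2. *Counted from the last dose (appendix footnotes, with the header's ± 5).* Day 23 to 33. Gap: 60 − 33 = 27 to 37 days, or 45% to 62%.
3. *End of Treatment Visit 7 days after the last dose (assumption: one weekly cobomarsen interval).* 7 + 23 = Day 30 to 7 + 33 = Day 40. Gap: 20 to 30 days, or 33% to 50%.

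No reading reaches Day 60. The latest possible Follow-up Visit differs by 47 − 33 = 14 days between readings 1 and 2.

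**Comparison groups.** For a non-progressor on a 4-weekly grid counted from the last dose, nominal contacts fall on Days 28, 56 and 84, so the end of the window is bracketed. A prompt crossover subject has visits on Days 1, 2, 3, 5, 8, 15, 22 and 29 and weekly from Week 6, so Day 60 after the last vorinostat dose is covered.

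**Drug persistence (cobomarsen only).** Fraction of a terminal-phase level remaining = 0.5^(t/h), with h = 17.5 or 21 days:

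| | Day 28 | Day 60 |
|---|---|---|
| h = 17.5 | 0.33 | 0.09 |
| h = 21 | 0.40 | 0.14 |

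This supports plausibility of late events and nothing more.

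**The case against.** The best defence is that the duty to report does not lapse at the Follow-up Visit. Section 10.5.1 records events volunteered by the subject, Section 10.6.1 keeps the 24-hour duty for serious events to Day 60, Sections 10.5.2 and 10.6.2 follow related and serious events to resolution or stabilization, Section 10.7 covers later events considered caused by treatment, and unscheduled visits are allowed. This stands: a reader might infer that the end of the window goes unobserved, but the documents show only that it has no planned contact. The appendices call for ongoing review of adverse events, and Section 8.4 sends all consenting subjects into follow-up, but neither names an occasion after the Follow-up Visit at which a progressor would be asked.

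Other limits also stand:

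- A reader might infer that all progressors, or most subjects, are affected. Prompt crossover subjects are not, and the documents give no figure for crossover uptake.
- The 37-day extreme needs an early Follow-up Visit and, under Section 8.6, an End of Treatment Visit on the day of the last dose. Reading 3 may be more typical for cobomarsen.
- The half-life is offered tentatively. The same section reports half-lives of 5.0 to 8.2 hours over the first 24 hours and no significant accumulation at 900 mg. It says nothing about vorinostat, and no late toxicity is documented.
- Section 5.3.1 sets contraception at "105 days after the last dose of cobomarsen or 180 days after the last dose of vorinostat". The 105 days equal five 21-day half-lives, but the protocol does not give that as the reason.
- No analysis of 60-day incidence, or by reason for stopping, is planned.
- Non-progressors who withdraw consent or start another MF treatment also leave scheduled follow-up, so the contrast with progressors is not absolute.

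**Conclusion.** The point holds for progressors who are not on crossover dosing. The plan requires collection to Day 60 but schedules their last contact on Day 23 to 47 (Day 23 to 33 on the footnote count), leaving 13 to 37 days to passive capture. The result assumes visits kept within their stated windows and no unscheduled contact. Because other subjects keep active review across Day 60, ascertainment depends on the reason for stopping and possibly on arm.

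A reader might go further and conclude that event rates are materially understated. Passive capture makes some loss likely in direction, but the documents give neither a late-event rate nor the numbers affected, so its size cannot be stated. This is a worthwhile, inexpensive improvement to safety collection and does not touch the efficacy analysis. The two starting points for the Follow-up Visit are a separate contradiction that needs resolving in any case.

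**What to change.** Add one telephone contact for adverse and serious adverse events at about Day 60 after the last dose to Sections 8.6 and 9.3.2 and Appendices B, C and E. Apply it to subjects who have not withdrawn consent, are not on crossover dosing and have no scheduled follow-up contact at or after Day 60. That wording also picks up non-progressors who leave follow-up on starting another MF treatment.

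Reconcile the starting point of the Follow-up Visit between Sections 8.6 and 9.3.2 and the column headers (End of Treatment Visit) on one side, and footnote a of Appendices B and E and footnote b of Appendix C (last dose) on the other.

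The cost is one call per affected subject and some schedule wording. Section 8.2.9 already allows telephone visits in the vorinostat group. Recorded adverse-event counts may rise slightly. No treatment rule, endpoint or sample size changes.
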